## **9 Discontinuation and completion**

### **9.1 Discontinuation from study treatment and from study**

#### **9.1.1 Discontinuation from study treatment**

Discontinuation of study treatment for a participant occurs when study treatment is permanently stopped for any reason (prior to the planned completion of study drug administration, if any) and can be initiated by either the participant or the investigator.

The investigator must discontinue study treatment for a given participant if, he/she believes that continuation would negatively impact the participant's well-being.

Discontinuation from study treatment is required under the following circumstances:

- participant/guardian decision
- participant no longer has an available study partner
- Pregnancy
- Use of prohibited treatment as per recommendations in the cohort-specific prohibited treatment section within [Section 17](#) and medications prohibited in the core protocol as stated in prohibited medication section within [Section 6.2.2](#). Any situation in which continued study participation might result in a safety risk to the participant
- Following emergency unblinding

- The investigator believes that continuation would negatively impact the safety of the participant or the risk/benefit ratio of trial participation
- Emergence of the following adverse events, that in the judgement of the investigator, taking into consideration the participant's overall status, prevent the participant from continuing participation in the study:
  - Severe lumbar puncture related complications such as meningitis
  - Severe neurological findings such as neuropathy
- Severe hypersensitivity reaction to study treatment occurs, including any of the following: anaphylaxis, fever, chills, urticaria, dyspnea, headache, myalgia, hypotension
- Any SAE, regardless of whether the event is suspected to be related to study drug
- Any severe adverse event that is suspected to be related to study drug (apart from liver and renal events - see below)
  - If a liver or renal event occurs, follow guidelines outlined in [Section 16.2](#) and [Section 16.3](#), respectively, regarding discontinuation of study treatment
- Presence of any malignancy, other than those allowed in study exclusion criteria
- Any clinically significant infection
- Any additional circumstance listed in the Cohort-specific [Section 17](#) as applicable to the participant's Cohort/study treatment assignment

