If discontinuation from study treatment occurs, the investigator should make a reasonable effort to understand the primary reason for the participant's discontinuation from study treatment and record this information.

Participants who discontinue from study treatment will be considered discontinued from the study and will be asked to return for the Early Termination Visit indicated in the Assessment Schedule ([Table 8-1](#)).

If the participant cannot or is unwilling to attend the Early Termination Visit, the site staff should contact the participant, or participant's caregiver by phone.. This telephone contact should preferably be done according to the study visit schedule for Early Termination Visit.

At a minimum, the following data should be collected during the telephone contact:

- New / concomitant treatments
- Adverse Events / Serious Adverse Events

The investigator must also contact the IRT to register the participant's discontinuation from study treatment.

If discontinuation occurs because treatment code has been broken, please refer to Emergency breaking of assigned treatment code [Section 6.6.3](#).

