### **9.5 Early study termination by the sponsor**

The study can be terminated by Novartis at any time for any reason. This may include reasons related to the benefit/ risk assessment of participating in the study, practical reasons (including slow enrollment), or for regulatory or medical reasons. In taking the decision to terminate, Novartis will always consider the participant welfare and safety. Should early termination be

necessary, participants must be seen as soon as possible and treated as a prematurely withdrawn participant. The investigator may be informed of additional procedures to be followed in order to ensure that adequate consideration is given to the protection of the participant's interests. The investigator or sponsor depending on the local regulation will be responsible for informing IRBs/IECs of the early termination of the trial.

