**canakinumab**

---

In patients with cardiovascular risk (CANTOS), there was a slight increased risk of serious infections, as well as fatal sepsis, fatal pneumonia and fatal respiratory tract infection, in patients treated with canakinumab compared with placebo. However, the overall incidence remains low.

In the large CANTOS study (>10,000 patients with cardiovascular risk), no tuberculosis reactivation was seen, and the overall frequency of reporting of opportunistic infections was low (0.1 - 0.2%) and balanced between patients on canakinumab and on placebo.

**Malignancy events** have been reported in patients treated with canakinumab during clinical development. However, in patients with cardiovascular risk (CANTOS), the overall incidence of malignancy AEs was numerically lower in the canakinumab groups compared with placebo and this was largely due to a lower incidence of lung cancer.

In inflammatory indications, the following **blood abnormalities** were observed: decreased white blood cell count and absolute neutrophil counts were reported.

In patients with cardiovascular risk (CANTOS), small decreases in mean neutrophil counts were seen in patients taking canakinumab, but most patients remained within the normal range.

Neutropenia was not associated with a greater risk of infections. In inflammatory indications, mild and transient decreases in platelet counts were observed at a higher incidence with canakinumab.

In patients with cardiovascular risk (CANTOS), a dose-dependent increase in thrombocytopenia AEs and CTC Grade 1 platelet count abnormalities was observed for canakinumab relative to placebo.

Grade 2 abnormalities occurred at low and comparable rates between canakinumab 150 mg group, while Grade 3 or 4 abnormalities were rare and rates were comparable across the treatment groups (0.4% of patients on 150 mg canakinumab and 0.4% of patients on placebo).

The cumulative post-marketing patient exposure since the first launch of the product was estimated to be 44475 patient-treatment years (cut-off 30-Jun-2020). A review of safety data at the cut-off date of this document did not reveal any new or changing safety-related information beyond the known safety profile of canakinumab. All the safety data remains in accord with the previous cumulative experience.

---

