In addition, a sub-set of these same participants (up to 22 per investigational agent/matching placebo) will undergo PET CCI imaging at baseline and following completion of the first 12 weeks treatment. Alterations in activated microglia and astrocytes due to therapeutic intervention will be measured using a PET CCI PET imaging in this subset of participants and analysis of CSF and/or serum samples in all participants will provide measures of both central and peripheral inflammation following treatment with an investigational agent/matching placebo. An interim analysis of the PET CCI and CSF soluble biomarker data may be conducted following completion of the first 12 weeks of treatment.

For each investigational agent, one or more interim analyses may be conducted, as appropriate, to support decision making concerning the sponsor's clinical development projects in general, or in case of any safety concerns. The results of these analyses will not have any impact on study conduct.

The study design is described in Figure 1-1.

Figure 1-1 Study design schematic

B = Baseline R = Randomization EOC = End of cohort

Randomization for any participant can occur after informed consent is obtained and eligibility is confirmed, ideally as close to Day 1 as possible. Participants will be randomized into any of the treatment arms open to enrolment for which the participant meets the eligibility criteria

Treatment arm(s) will be defined for each cohort.

EOC2 visit only required for an extended half-life. For all other treatments, EOC1 will serve as End of Cohort visit.

Approximately n=86 participants were planned to be randomized in a 1:1 ratio (active:placebo) using an IRT system. The study was prematurely terminated after 34 participants randomized due to sponsor's decision.

The primary endpoint is the change in NTB total z-score at week 24.

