In rare cases where multiple measurements meet the baseline definition, with no further flag or label that can identify the chronological order, then the following rule should be applied: If values are from central and local laboratories, the value from central assessment should be considered as baseline. If multiple values are from the same laboratory (local or central) or collected for ECGs or vital signs, then the median should be considered as baseline.

If participants have no value as defined above, the baseline result will be missing.

For safety parameters other than ECG, scheduled pre-dose collections as well as unscheduled collections on Day 1 for which no time is available will be considered as pre-dose.

For ECG, if dosing time on study Day 1 or ECG time for scheduled pre-dose ECGs is missing, the pre-dose ECG will be considered as baseline. If a scheduled pre-dose measurement actually occurred post-dose, then the corresponding measurement will be treated and analyzed similar to an unscheduled post-dose measurement.

Unscheduled Assessment:

In general, descriptive summary statistics will not include unscheduled/repeat assessment.

For all analyses regarding abnormal assessments or analyses based on worst post–baseline value (e.g. laboratory, ECGs, vital signs), all post-baseline values will be included (scheduled, unscheduled, repeat). All unscheduled and repeat measurements will be included in listings.

Analysis visit window:

No time-window will be applied in this study.

In summary by visit the scheduled EOC1 and EOC2 (if available) visit will be included.

On-treatment assessment/event

The overall observation period will be divided into 2 mutually exclusive segments:

- 1. *pre-treatment period*: from day of participant's informed consent to before date/time of first administration of study treatment
- 2. *on-treatment period*: from date/time of first administration of study treatment to the last visit date EOC1 (or EOC2 if applicable)

Note: If dates are incomplete in a way that clear assignment to pre-, on-, post-treatment period cannot be made, then the respective data will be assigned to the on-treatment period.

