2.7.1 Adverse events (AEs)

All information obtained on adverse events will be displayed by treatment and participant.

The number (and percentage) of participants with treatment emergent adverse events (events started after the first dose of study medication or events present prior to start of study treatment but increased in severity based on preferred term) will be summarized in the following ways:

- by treatment, primary system organ class and preferred term.
- by treatment, primary system organ class, preferred term and maximum severity.

Separate summaries will be provided for study drug related adverse events, death, serious adverse events, other significant adverse events leading to discontinuation.

A participant with multiple adverse events within a primary system organ class is only counted once towards the total of the primary system organ class.

In AE summaries, the primary system organ class will be presented alphabetically and the preferred terms will be sorted within primary SOC in descending frequency. The sort order for the preferred term will be based on their frequency in all participants.

In addition, for EudraCT requirements a summary of (1) Serious AEs and deaths, with number of occurrences and (2) Non-serious AEs, with number of occurrences will be produced (an occurrence is defined as >1 day between start and prior end date of record of same preferred term).

2.7.2 **Deaths**

All deaths will be listed using Safety set and post treatment deaths will be flagged. A separate listing of deaths prior to starting treatment will be provided for all screened participants.

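### Adverse-event percentages ignore time observed, so events after a harm-driven stop can be under-counted in the arm with more such stops

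*SAP*

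**What the plan says.** SAP 2.7.1 reports "The number (and percentage) of participants with treatment emergent adverse events" by treatment, system organ class, preferred term and maximum severity, using the safety set (everyone who received study drug). Related events, deaths, serious events and events leading to discontinuation get separate summaries. The registry tables add occurrence counts. None of these is divided by time. SAP 2.4.1 summarises duration of exposure by arm but does not link it to adverse events.

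SAP 2.1.1 counts events "from date/time of first administration of study treatment to the last visit date EOC1 (or EOC2 if applicable"). It does not mention the Early Termination Visit.

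Protocol 9.1.1 requires treatment to stop after any serious adverse event, a severe related event, severe hypersensitivity, or "Any clinically significant infection", among other reasons. It continues: "Participants who discontinue from study treatment will be considered discontinued from the study and will be asked to return for the Early Termination Visit". Table 8-1 puts that visit 30 days after the last dose. Cohort 1 completers are seen at EOC2 on Day 281 (SAP 1.1, protocol 17.1.1).

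Other passages ask for longer follow-up. Protocol 10.1.1 wants adverse-event monitoring for the longest of 30 days, five half-lives or the end of study visit. Protocol 4.5 wants adverse-event data up to the end of cohort date, although it refers to 9.1.1 for early discontinuation. Protocol 10.1.3 limits reporting of serious events regardless of cause to 30 days after the last dose.

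**The concern.** A crude percentage compares arms fairly when both are observed for similar lengths of time. Here the length depends partly on harm. A participant stopped after a serious event or an infection may be seen for a fraction of a completer's time, and anything that happens later goes uncounted. Randomisation balances administrative truncation in expectation, but not stops that the treatment itself causes.

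The protocol gives a reason to think that stops could differ by arm. Infection is a stop trigger, and Table 17-1 reports that in the large cardiovascular trial of canakinumab "there was a slight increased risk of serious infections, as well as fatal sepsis" compared with placebo. If canakinumab causes more stops, the crude tables would favour it in the rows that do not contain the trigger.

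Safety versus placebo is called a key secondary objective (SAP 2.6). It is also one of the main outputs left: "The study was prematurely terminated after 34 participants randomized due to sponsor's decision", and SAP 2.6.3 reduces the PET data to a listing of one participant.

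**Working it through.** The documents give no adverse-event rate and no harm-driven stop rate, so there is no figure of the plan to reproduce. The check is an illustration.

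**Inputs from the documents**
- Completer's last visit: Day 281.
- Early stopper's visit: last dose + 30 days (Table 8-1).
- Five half-lives: 5 × 26 = 130 days (Table 17-1).
- Drop-out: 15% overall (SAP 3.1), not split by arm or reason.
- Size: 34 randomised 1:1, so about 17 per arm (actual split not stated).

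**Assumptions**
- Constant hazard and a 30% risk over 281 days for one adverse event.
- Stops after the Day 57 dose, triggered by something other than the event being counted.
- 25% stop on active and 5% on placebo, which averages to the stated 15%.

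**Step 1: time observed.** A stopper is seen to T = 57 + 30 = 87 (31% of 281) or T = 57 + 130 = 187 (67%).

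**Step 2: formula.** h = −ln(0.70)/281 = 0.001269 per day. With q the share stopping, crude proportion = (1 − q)(1 − e^(−281h)) + q(1 − e^(−Th)).

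**Step 3: no true difference between arms.** For T = 87, active = 0.75 × 0.300 + 0.25 × 0.1045 = 0.251 and placebo = 0.95 × 0.300 + 0.05 × 0.1045 = 0.290.

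| Stoppers followed to | T | Risk by T | Active | Placebo | Crude ratio |
|---|---|---|---|---|---|
| Last dose + 30 days | 87 | 10.5% | 25.1% | 29.0% | 0.87 |
| Last dose + 130 days | 187 | 21.1% | 27.8% | 29.6% | 0.94 |
| EOC2 | 281 | 30.0% | 30.0% | 30.0% | 1.00 |

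With 20% versus 10% stopping, the ratios are 0.93, 0.97 and 1.00.

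**Step 4: true rate ratio 1.5.** With 25% versus 5% stopping, the crude ratio is 0.349/0.290 = 1.20 (30 days) or 0.386/0.296 = 1.30 (130 days), against 0.414/0.300 = 1.38 under full follow-up.

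**Step 5: size in participants.** In step 3 with 30-day follow-up, the active arm loses 30.0 − 25.1 = 4.9 points, and 0.049 × 17 = 0.8 of a participant. Over assumed risks of 10–50%, stop rates of 5–30% and last doses from Day 1 to Day 85, the loss within an arm is 0.3–12.8 points (30 days) or 0.1–6.7 points (130 days). The extreme is about 2 of 17 participants.

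**Step 6: effect of a time denominator.** Under a constant hazard, expected time at risk up to the first event is the crude proportion divided by h. First events per participant-time therefore return h whatever q and T are, and the rate ratio is 1.00 in step 3 and 1.50 in step 4.

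**Step 7: which rows are affected.** A participant stopped by an infection is already in the any-event and infections rows, and in the serious and discontinuation summaries where those apply. Later events of the same kind cannot change a once-per-participant count. What can be lost is an event in another class or preferred term, or a more severe later episode.

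**The case against.** A reader might infer that a drug which causes stops is shown with too few adverse events overall. The documents do not support that. The triggering event is counted, and SAP 2.7.1 tabulates serious events, deaths and events leading to discontinuation separately. The signal that would drive the stops stays visible.

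The 30-day cut is not settled either. Protocol 10.1.1 and 4.5 ask for more, and if stoppers were followed to EOC2 the distortion would be zero. Against that, Table 8-1 schedules nothing for a stopper after the 30-day visit, and under the 130-day rule the distortion shrinks but does not vanish.

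The unequal stop rates are assumed. In the illustration the gap of 29.0 − 25.1 = 3.9 points is small beside the sampling error of a difference at 30% risk, √(2 × 0.3 × 0.7/17) ≈ 16 points. This limits the importance of the point, although sampling error does not cancel a systematic shift.

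The sponsor's termination is not itself a source of directional bias. Protocol 9.5 says "participants must be seen as soon as possible and treated as a prematurely withdrawn participant", but that truncation is balanced between arms in expectation. If it kept some participants from reaching Day 281, the contrast with stoppers would be smaller than shown here.

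Disposition with reasons, exposure by arm and participant listings with study day let a careful reader of 34 records see who stopped and when, and no formal adverse-event test is planned. This helps, but no table shows time observed beside the counts. Nor is dosing time the same as observation time: a completer is followed for 281 − 141 = 140 days after the last dosing visit.

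Finally, rates would be imprecise. With five first events per arm, the 95% interval for a rate ratio extends by a factor of exp(1.96 × √(1/5 + 1/5)) ≈ 3.5 either way. That is a good reason not to make rates the sole basis for comparing arms.

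**Conclusion.** The point holds in a limited form. The tables take no account of time observed, and protocol 9.1.1 with Table 8-1 shortens observation after harmful events. If stops of this kind are more frequent in one arm, that arm's counts are too low for events arising after the stop, in other system organ class and preferred term rows and in maximum severity. The rows containing the trigger are not lowered by that kind of stop.

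The size cannot be known from the documents. On the stated assumptions the crude ratio is 0.87, 0.94 or 1.00 when the truth is 1.00, depending on which follow-up passage governs, and the loss is usually one participant or fewer per row. This is a moderate reporting gap that is cheap to close. It does not show that harm will be hidden.

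**What to change.** 1. In SAP 2.7.1 keep n (%) and show total and median follow-up time by arm in the adverse-event tables.
2. Add, as a companion display and not a replacement, exposure-adjusted first-event incidence by arm with a confidence interval: participants with a first event divided by participant-time from first dose to first event or last contact. Give it for any treatment-emergent event, serious events, and each system organ class including infections. The any-event and serious rows are worth including because stops for other reasons also shorten observation there.
3. In SAP 2.1.1 state when the adverse-event period ends for a participant who stops early. The section defines only a pre-treatment and an on-treatment period, yet later refers to a post-treatment one.
4. Reconcile protocol 9.1.1, Table 8-1 and 10.1.3 with protocol 10.1.1 and 4.5 on how long adverse events are followed after an early stop. Report which rule was applied.

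The cost is SAP wording and a few table columns from dates already collected. The downside is that the rates assume a roughly constant hazard, which is doubtful when completers contribute months after the last dose, and they will be imprecise with 34 participants.

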2.7.3 Laboratory data

All laboratory data will be listed by treatment group, participant, and visit/time and if normal ranges are available abnormalities will be flagged. Summary statistics of values and changes from baseline will be provided by treatment and visit/time.

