**Adverse events**

All information obtained on adverse events will be displayed by treatment group and participant.

The number (and percentage) of participants with treatment emergent adverse events (events started after the first dose of study medication or events present prior to start of double-blind treatment but increased in severity based on preferred term) will be summarized in the following ways:

- by treatment, primary system organ class and preferred term.
- by treatment, primary system organ class, preferred term and maximum severity.

Separate summaries will be provided for study medication related adverse events, death, serious adverse events, other significant adverse events leading to discontinuation.

The number (and proportion) of participants with adverse events of interest will be summarized by treatment.

A participant with multiple adverse events within a primary system organ class is only counted once towards the total of the primary system organ class.

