**Clinical laboratory evaluations**

All laboratory data will be listed by treatment group, participant, and visit/time and if normal ranges are available abnormalities will be flagged. Summary statistics will be provided by treatment group and visit/time.

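### The SAP omits, undeclared, the protocol's adverse-events-of-interest summary and plans no by-arm count of laboratory threshold crossings, so these are counted by arm only if reported as adverse events

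*SAP*

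**What the plan says.** **Adverse events.** Under adverse events, protocol 12.5.2 states: "The number (and proportion) of participants with adverse events of interest will be summarized by treatment". SAP 2.7.1 carries over the text around that sentence but not the sentence itself. It keeps counts "by treatment, primary system organ class and preferred term", the same by maximum severity, and this line: "Separate summaries will be provided for study drug related adverse events, death, serious adverse events, other significant adverse events leading to discontinuation". In its visible text, SAP Section 4 (changes to protocol-specified analyses) mentions only the cancelled interim analysis.

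**Laboratory data.** SAP 2.7.3 has two elements. The first is a listing: "All laboratory data will be listed by treatment group, participant, and visit/time and if normal ranges are available abnormalities will be flagged". The second is a summary: "Summary statistics of values and changes from baseline will be provided by treatment and visit/time". Protocol 12.5.2 is no fuller on the summary: "Summary statistics will be provided by treatment group and visit/time".

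**Which values enter.** SAP 2.1.1 says: "In general, descriptive summary statistics will not include unscheduled/repeat assessment". It then provides that analyses of abnormal or worst post-baseline values use every post-baseline value, whether scheduled, unscheduled or repeat, and it names laboratory data among the examples.

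**Risks and alerts.** Protocol Table 17-1 lists blood abnormalities among the selected risks of canakinumab. For the cardiovascular-risk trial it reports that "a dose-dependent increase in thrombocytopenia AEs and CTC Grade 1 platelet count abnormalities was observed". Table 16-1 defines liver triggers. Section 10.2.2 and Table 16-5 define renal alerts.

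**The concern.** Comparing safety with placebo is a secondary objective, and both protocol 4.3 and SAP 2.6 describe safety as key. The protocol's cited experience in older patients is with 300 mg every 12 weeks (17.1.2.3), while cohort 1 moves to 300 mg every 4 weeks. Because the trial stopped at 34 participants, the safety tables are among its more useful outputs.

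A reader of the report would want to know how many participants in each arm had a low neutrophil or platelet count, met a liver trigger or met a renal alert. The SAP specifies no table that answers this from the laboratory values. It also loses, without comment, the one summary in which the protocol intended to gather events of special concern by treatment.

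**Working it through.** No stated figure is in dispute. The check compares the texts and then adds a small illustration.

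**Step 1. Analyses specified by data type**

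| Data | Listing | By-visit statistics | By-arm n (%) beyond a limit |
|---|---|---|---|
| ECG (SAP 2.7.4.1) | yes | yes | yes, notable values |
| Vital signs (SAP 2.7.4.2) | yes, with notable limits | yes | no |
| Laboratory (SAP 2.7.3) | yes, flagged against normal ranges | yes | no |
| Adverse events of interest (protocol 12.5.2) | – | – | planned in the protocol, absent from SAP 2.7.1 |

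The all-values rule in SAP 2.1.1 thus has no laboratory analysis to act on.

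**Step 2. Where an abnormal value can appear**

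- *It meets the adverse event criteria.* Protocol 8.4.2 requires it to be reported, and SAP 2.7.1 counts it by arm. The criteria in 10.1.1 are that it causes signs or symptoms, is considered clinically significant, or requires therapy.
- *It is seen at a scheduled visit but not reported as an adverse event.* It enters the by-visit statistics. Under the default in SAP 2.1 these include minimum and maximum, so an extreme can be seen. The number of participants beyond a limit cannot.
- *It is seen only at an unscheduled or repeat draw and not reported as an adverse event.* Under 2.1.1 it generally enters no summary and appears only in the flagged listing.

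**Step 3. Size of the effect on a visit mean**

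Inputs: 34 randomised (SAP 1.1) and a 1:1 ratio. I assume an equal split with all participants treated, so 34/2 = 17 per arm. The abnormal values below are illustrative, with every other participant in the arm unchanged.

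- Count table: one participant is 1/17 = 5.9% of the arm.
- ALT rising from 1 to 8 times the upper limit of normal (ULN) in one participant: the arm mean moves by (8 − 1)/17 = 0.41 × ULN.
- Creatinine up 50% in one participant: the mean percent change moves by 50/17 = 2.9 points.
- Neutrophils down 3.0 × 10⁹/L in one participant: the mean moves by 3.0/17 = 0.18 × 10⁹/L.

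**Step 4. What a count table could show at this size**

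The chance of at least one event in an arm of 17 is 1 − (1 − p)^17.

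| Assumed true rate p | Chance of at least one event |
|---|---|
| 1% | 16% |
| 2% | 29% |
| 5% | 58% |
| 10% | 83% |

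A count of 0/17 has a one-sided 95% upper bound of 1 − 0.05^(1/17) = 16.2%. The table would be descriptive and could not rule out an uncommon effect.

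**The case against.** The case on the other side is substantial, and it defeats several stronger readings.

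- *A reader might infer that cytopenias and liver or renal events are never counted by arm.* They are counted when reported as adverse events, by preferred term and by severity. Table 16-3 directs that an adverse event be recorded for isolated bilirubin above 3 × ULN.
- *A reader might infer that an imbalance would be visible only in listings.* Scheduled extremes show as a visit minimum or maximum. A repeat drawn to confirm an alert does not remove the scheduled value that raised it. With 34 participants, the listing by treatment group can also be counted by hand.
- *A reader might infer that the SAP cut back the protocol's laboratory plan.* It did not. The protocol plans the same listing and by-visit statistics, and the SAP adds changes from baseline. Only the adverse-events-of-interest summary was lost.
- *A reader might infer that the lost table would have covered blood counts and liver or renal triggers.* The visible text never defines adverse events of interest, so this cannot be shown. The Safety Surveillance Plan and the separate programming specifications were not available.
- *A reader might take Table 17-1 as evidence that cytopenias would be split across system organ classes.* Its entries are reference lists for different indications. The table adopted for this study is the cardiovascular one, which adds no further classes.

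The objection does not dispose of two facts. A protocol-planned by-arm summary is missing from the SAP and its removal is undeclared. Threshold crossings not reported as adverse events also have no by-arm count. The adverse event route depends partly on investigator judgement, and mild abnormalities, such as the Grade 1 platelet findings in Table 17-1, may not meet the criteria.

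**Conclusion.** The point holds in this limited form and should be acted on. SAP 2.7.1 omits the adverse-events-of-interest summary without declaring it. SAP 2.7.3 specifies no by-arm n (%) of participants whose worst post-baseline value meets a blood-count limit, a Table 16-1 laboratory liver trigger or a 10.2.2 renal alert, although SAP 2.1.1 provides the data rule for such analyses and ECG receives counts.

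The consequence is incomplete safety reporting; no planned figure or test is wrong. One affected participant in an assumed arm of 17 would be 5.9% in a count table, but would move a visit mean only slightly, or not at all if the value came from an extra draw. The conclusion rests on the visible text and on the equal-split assumption. If the separate specifications already contain these tables, the remaining work is to state them in the SAP.

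**What to change.** 1. **SAP 2.7.1 and Section 4.** Define the adverse events of interest for cohort 1 and restore the by-treatment n (%) table. Otherwise, declare and justify its removal in Section 4.

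2. **SAP 2.7.3.** Add a by-treatment n (%) table of participants by worst post-baseline value, using all scheduled, unscheduled and repeat values as 2.1.1 provides. Tabulate against:
   - the laboratory liver triggers in Table 16-1;
   - the renal alerts in 10.2.2 and Table 16-5, stating whether a single or a confirmed value counts;
   - prespecified neutrophil, leukocyte and platelet categories.

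3. **Blood-count categories.** If the protocol's entry limits are borrowed (neutrophils below 1.5 × 10⁹/L, platelets below 100,000/mm³), label them as reporting categories only. They are eligibility criteria, not on-treatment alerts. The protocol states two white-cell limits, 3000/mm³ in the core criteria and 3.5 × 10⁹/L for cohort 1, so the SAP should say which one the table uses.

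The cost is SAP wording and two tables from data already collected, with a small programming effort. Sample size, alpha and clinical rules do not change.
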